	
optimum design, there would be a 90.7% chance of detecting a tumor response rate of at least 40% and a response rate of 15% or less would lead to the conclusion that the regimen lacks antitumor activity at a 0.05 significance level. The probability of early stopping (in stage I) is 0.058 if the true response rate of the combination is 40%.
 
Dose Schedule
 
Loading phase: Patients will receive selinexor at 80 mg on D-7 orally. This dose was shown to be tolerable in a study of patients with chronic hematologic malignancies including myeloma (NCT01607892). In addition, patients will receive dexamethasone 40 mg on day -7. The loading phase lasts 1 week.
 
Induction phase: Patients will be treated initially with selinexor at the RP2D PO weekly dose (on days 1, 8, 15) (or twice weekly dosing on cohort 3m and 4m), liposomal doxorubicin at the RP2D IVPB on D1 (at least 2 hours (and no longer than 4 hours) after the selinexor dose), and dexamethasone 40 mg PO weekly (on days 1, 8, 15). Cycles are repeated every 3 weeks (21 days) and patients will receive a maximum of 8 cycles of therapy with this combination. For patients with prior doxorubicin exposure, after a total dose of 450 mg/m^2, patients will be required to have cardiac assessments (echocardiograms or MUGA) every 2 cycles. Any patient with a decrease in ejection fraction of <math>\geq</math> 20% from baseline will have LD discontinued.
 
Maintenance phase: After 8 cycles of therapy with selinexor, LD and dexamethasone, patients will be eligible to proceed on maintenance with the tolerated dose of selinexor and dexamethasone until disease progression. Cycles are repeated every 28 days
 
Discontinuation Criteria:
 
At the discretion of the Investigator, the investigator may remove a patient from the study for the following reasons:
 

• Due to disease progression

• Noncompliance with study procedures

• Patient no longer consents to participate in the study

• Intercurrent illness that interferes with study assessments

• Investigator discretion

• Incidence or severity of AEs in this study indicates a potential health hazard to the patient

• Termination of the study by the sponsor

--	---

	
 
• Pregnancy
 

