## **3 INVESTIGATIONAL PLAN**

### **3.1 Overview of Study Design and Dosing Regimen**

This is a investigator-sponsored phase I/II study to evaluate the effectiveness and tolerability of oral selinexor in combination with liposomal doxorubicin and dexamethasone in patients with relapsed and refractory multiple myeloma. This study will be conducted at H. Lee Moffitt Cancer Center and Research Institute, Wayne State University / Karmanos cancer center and Virginia Commonwealth University Massey Cancer Center.

After the initial screening visit and registration in the study, eligible patients will receive selinexor on day -7= at a dose of 80 mg in addition to dexamethasone 40 mg. After 1 week of dosing with selinexor and dexamethasone, patients will receive weekly selinexor at a starting dose of 80 mg (cohort 2m) in combination with liposomal doxorubicin at a starting dose of 20 mg/m^2, and dexamethasone at 40 mg orally weekly.

[figure not shown]
During the treatment period, patients will undergo physical examination and assessment of tumor response (paraprotein assessment) every 3 weeks per the IMWG uniform response criteria.

Patients will be treated until progression of disease or the development of unacceptable toxicities. All patients will then undergo a final visit (end of treatment visit).

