#### 6.3.2 Removal of Patients from Treatment

Subjects will be free to discontinue treatment or withdraw from the study at any time, for any reason, or they may be withdrawn/ removed if necessary in order to protect their health (see reasons for withdrawal below). It is understood by all concerned that an excessive rate of withdrawals can render the study uninterpretable; therefore, unnecessary withdrawal of subjects should be avoided.

Patients will be removed from further treatment for the following reasons:

- Disease progression
- Non-compliance with visits and assessment which indicates a potential health hazard to the patient
- Patient no longer consents to participate in the study
- Intercurrent illness that interferes with study assessments
- Incidence or severity of AEs in this study indicates a potential health hazard to the patient
- Investigator discretion

- Pregnancy
- Termination of the study by the sponsor

If there is a medical reason for withdrawal of treatment, the patient will remain under the supervision of the investigator until the AEs have been resolved or declined to baseline values.

In case of premature discontinuation of the study treatment, the investigations scheduled for the EOT should be performed, if possible. Should a patient decide to withdraw, every effort will be made to complete and report the observations as thoroughly as possible. The investigator should contact the patient to determine as completely as possible the reason for the withdrawal. A complete final evaluation at the time of the patient's withdrawal should be made, with an explanation of why the patient is withdrawing from the study. If the reason for removal of a patient from the study is an adverse event or an abnormal laboratory test result, the principal specific event or test will be recorded on the case report form.

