**8.1.3 Dose Modifications for Selinexor**

Based on observations from the ongoing Phase I studies in patients with advanced hematological and solid tumors, selinexor shows a reasonably wide therapeutic range, with activities from ~12mg/m^2 to 35mg/m^2. At the present time, we do not know how to predict which patient's tumors will respond to lower doses, nor can we predict tolerability. Therefore, in order to optimize specific anti-tumor activity and the patient's tolerability, therapy is initiated at 80mg weekly. In patients with tolerability issues on selinexor, we recommend reducing the selinexor dose. In addition, if patient is experiencing one or more Grade ≤2 toxicities such as fatigue or anorexia, then 1-2 doses of selinexor can be held, and dosing resumed at current dose.

Toxicity will be graded according to NCI CTCAE, version 4.03; the therapy modifications described below are applied according to this severity grading. If drug-related toxicity requires a treatment delay of more than 4 weeks, then the patient is taken off protocol treatment. Each dose modification or treatment delay has to be documented in the CRF, including the respective reason.

Phase I data in patients with both solid and hematologic malignancies indicate that selinexor is associated with minimal laboratory abnormalities. Therefore, provided that it is clinically indicated, patients should be treated aggressively with supportive care to reduce

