Grade 1 or 2	Maintain dose level and initiate standard supportive care.
Grade 3	Delay dose until resolved to $\leq$ Grade 1, then reduce by 1 dose level
Grade 4	Discontinue selinexor and rule out other causes. If other causes of Grade 4 adverse event are uncovered, selinexor may be re-initiated at 1 dose level reduction.

All dose modifications should be based on the worst preceding toxicity.
 
Isolated values of <math>\geq</math> grade 3 alkaline phosphatase values will NOT require dose interruption. Determination of liver vs. bone etiology should be made, and evaluation of GGT, 5'NT, or other liver enzymes should be performed.
 
<math>\geq</math> Grade 3 anemia judged to be a hemolytic process secondary to study drug will require interruption of study treatment until resolved to <math>\leq</math>Grade 1. Selinexor may then be re-instituted at 2 levels below original dose.
 
<math>\geq</math> Grade 3 lymphopenia considered clinically significant will require dose interruption until resolved to <math>\leq</math> grade 2, then reduce by 1 dose level.
 
Patients are allowed dose reductions to a minimum dose of 5mg/m^2. If a patient requires a dose interruption of > 28 days, then the patient must be discontinued from the study. Patients who discontinue the study for a study related adverse event or abnormal laboratory value must be followed at least once a week for 28 days and subsequently at 28 day intervals until resolution or stabilization of the event, whichever comes first.
 
a. Common Terminology Criteria for Adverse Events (CTCAE Version 4.03 ) otherwise specified values.
	

- For all  $\geq$  Grade 3 hematological or non-hematological AEs that are NOT selinexor related: After consultation with the principal investigator and at the discretion of the treating physician, selinexor dosing may be maintained provided that the patient can continue to take the agent by mouth, or via other enteral route.

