### **11.6 Analysis of the Phase II**

For the primary endpoint in Phase II trial, we are interested in comparing the overall response rate of this combination with historical efficacy data using liposomal doxorubicin and dexamethasone in patients with relapsed and refractory myeloma. The overall response rate and its 95% confidence will be calculated using the method proposed by Atkinson and Brown[49]. This confidence interval takes into account the nature of the two-stage Simon design.

The secondary endpoints include progression-free survival (PFS), overall survival (OS), safety, and duration of response. Patients will be followed for survival and progression until termination of the study. PFS is defined as the time from start of treatment to death of any cause, disease progression, or the date of last follow-up, whichever comes first. OS is defined as the time from start of treatment to death of any cause or the date of last follow-up, whichever comes first. The time-to-event data will be estimated using the Kaplan-Meier method. The median of PFS and OS and 95% confidence intervals will be computed. The effect on time-to-event data adjusting for other factors (such as age and tumor stage) will be analyzed using the Cox proportional hazards regression models.

As the exploratory endpoints, the association between the change of each biomarker (e.g., nucleus to cytoplasm ratio, p53, CRM1, I $\kappa$ B and NF $\kappa$ B) from screening to day 1 of cycle 1 and the response to the therapy will be examined by the Satterthwaite t-test or the Wilcoxon rank sum test. The appropriate transformation such as log-transformation may be considered if necessary. In addition, we will examine if the disease progression is associated with the change from screening to date of progression or from day 1 of cycle 1 to date of progression. No multiplicity adjustment is planned due to the nature of exploratory study. A two-sided p-value of < 0.05 will be considered significant. We expect that 12 or more of 29 patients in Phase II are responders. With a two-sided significance level of 5%, 29 samples will provide 80.4% power to detect an effect size (mean difference divided by standard deviation) of 1.2 when the numbers of responders and non-responders are 12 and 17, respectively.

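### Section 11.6 promises survival and progression follow-up to study termination, but the conduct sections stop at the end of treatment visit and the exit rules mix leaving treatment with leaving the study; OS is then exposed to prognosis-linked censoring

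*Combined protocol and SAP*

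**What the plan says.** **The commitment.** Section 11.6 (Analysis of the Phase II) says: "Patients will be followed for survival and progression until termination of the study". The same section measures OS from start of treatment to death or last follow-up and estimates it by Kaplan-Meier. OS, PFS and duration of response are secondary endpoints (11.1.2).

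**The conduct sections.**
- Section 3.1 ends the patient's course with the EOT visit.
- Section 3.1.1 names four phases: screening, loading, induction and maintenance.
- The last calendar column (Section 5) is the EOT visit. Section 6.2.3 puts it 30 days (± 7) after the last study drug.
- Section 6.1.1 sets disease assessments for the treatment period, and 6.2.3 adds one at EOT.
- The synopsis labels the final visit as end of study, and 6.3.1 treats EOT as the point where the study is complete.
- Section 3.2 ends its timeline when the last patient leaves study treatment.

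**The exit rules.**
- Synopsis: "At the discretion of the Investigator, the investigator may remove a patient from the study for the following reasons". Progression is on that list.
- Section 6.3.2, with a nearly identical list: "Patients will be removed from further treatment for the following reasons". A later sentence of 6.3.2 covers the case where "the reason for removal of a patient from the study is an adverse event or an abnormal laboratory test result".
- Section 8.1.3, toxicity delay of more than 4 weeks: "then the patient is taken off protocol treatment".
- Table 2 notes, interruption of more than 28 days: "then the patient must be discontinued from the study".
- The Table 2 notes keep contact with patients who leave for a related adverse event or laboratory value: weekly for 28 days, then "subsequently at 28 day intervals until resolution or stabilization of the event". No survival contact is scheduled.

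**The concern.** A site working from the calendar, 6.3.1 and the synopsis label can reasonably close a patient at EOT. A site working from 11.6 keeps contact. Both are following the protocol. The problem is therefore a conflict between stated texts as well as a missing interval, and a follow-up contact that is nowhere scheduled is hard to monitor as a deviation.

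If EOT is the last contact, it becomes the OS censoring date. Treatment runs until progression or unacceptable toxicity (3.1), so this censoring is linked to prognosis, whereas Kaplan-Meier assumes that it is not. Patients would leave the risk set about a month after stopping, often just after progression. If they then die at a higher rate than patients still on treatment, the survival curve is too high. Survival contacts that are missed may not be recoverable later.

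PFS and duration of response are exposed only in patients who stop without progression. The primary response rate is not exposed.

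**Working it through.** **1. Texts side by side**

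| Event | Leaves treatment | Leaves the study |
|---|---|---|
| Listed reasons, including progression | 6.3.2 lead-in | Synopsis list (permissive) |
| Delay or interruption over 4 weeks / 28 days | 8.1.3 (toxicity delay) | Table 2 notes |
| Adverse event or laboratory result | 6.3.2 list (AE incidence or severity) | 6.3.2, later sentence |
| Final visit | 3.1, 6.2.3 | Synopsis label, 6.3.1 |

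No text sets a survival contact after EOT.

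**2. Direction of the bias**

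The documents give no OS figure, so there is none to reproduce. Let *a* be the rate of stopping treatment, *d* the death hazard on treatment, *b* the death hazard afterwards, and *p* the share of patients closed 30 days after the last dose.

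- On treatment and alive: A(t) = exp(−(a+d)t).
- Off treatment and alive: B(t) = a[exp(−bt) − exp(−(a+d)t)]/(a+d−b).
- True survival: A + B.
- Let L(t) be the part of B that stopped within the last 30 days. The hazard Kaplan-Meier sees is h = [dA + b((1−p)B + pL)] / [A + (1−p)B + pL].
- Its large-sample limit is exp(−∫h).

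The observed hazard is a weighted average of *d* and *b*, and closing patients removes weight from *b*. So OS is overstated if b > d, unbiased if b = d, and understated if b < d.

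**3. One case by hand**

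Take 4 months median on treatment, 8 months median afterwards and no deaths on treatment: a = ln2/4 = 0.1733, b = ln2/8 = 0.0866, d = 0. At 12 months A = 0.125 and B = 2 × (0.3536 − 0.125) = 0.457, so true survival is 0.582. L = 0.022.
- True hazard: 0.0866 × 0.457/0.582 = 0.068 per month.
- Hazard seen with half closed: 0.0866 × 0.240/0.365 = 0.057 per month.

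Integrated over time, 12-month OS reads 0.653 instead of 0.582.

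**4. Range**

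All inputs are assumed: median 4 months on treatment; survival after treatment with median 4, 8 or 12 months; on-treatment death-time median 15 months, 30 months, or no deaths on treatment. Triples follow the order 4, 8, 12.

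| On-treatment death-time median | True median OS (months) | Excess, one third closed | Excess, half closed |
|---|---|---|---|
| No deaths | 9.7, 14.2, 18.3 | 1.07, 1.19, 1.22 | 1.92, 2.14, 2.19 |
| 30 months | 8.4, 12.1, 15.5 | 0.70, 0.69, 0.60 | 1.23, 1.23, 1.07 |
| 15 months | 7.4, 10.4, 13.1 | 0.45, 0.35, 0.16 | 0.78, 0.60, 0.28 |

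The excess in 12-month OS runs from 0.5 to 5.6 percentage points with one third closed, and from 0.8 to 9.7 points with half closed.

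Sign checks: with equal hazards (both medians 12 months) the median is 12.0 with and without closure. With a lower later hazard (6 months on treatment, 12 after) and half closed, it reads 7.3 instead of 7.9.

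**5. Other endpoints**

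Assume median PFS of 4 months, 20% stopping for toxicity, and a progression hazard after stopping of 1 to 3 times that on drug. Median PFS is then overstated by 0 to 0.07 months if half of these patients are lost, and by 0 to 0.14 if all are. Of the 12 responders expected in 11.6, 0.7 to 1.0 have duration of response censored early if half are lost, and 1.4 to 2.0 if all are.

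**The case against.** **The commitment exists.** Section 11.6 requires follow-up, and 6.1.1, a conduct section, lists PFS, OS and duration of response among the efficacy evaluations. The opening of 6.3.2 separates stopping treatment from withdrawing from the study. Section 6.3.1 concerns later therapy and does not tell sites to stop collecting data, and the synopsis list is permissive. One central database, regular cross-site calls and central monitoring (14.1, 14.3) make site-by-site divergence less likely. The case report forms and the network handbook are not among the documents, so a survival form may exist. All of this stands. It means that the share of patients closed at EOT is unknown; it does not supply an interval or resolve the conflicting labels.

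**The bias may be small.** With no deaths on treatment, the large-sample standard error of median OS in 29 patients is roughly 1.7 to 3.5 months. The one-third-closed excess is below that, and OS carries no decision rule. This also stands, and it limits the point to the quality of a secondary estimate.

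**Stronger readings that the documents do not support.** A reader might infer that OS will be overstated. That needs both closure at EOT and a higher death hazard after treatment. The hazard condition is the expected one where stopping mostly marks progression, but it is stated nowhere. A reader might also infer that every patient is lost at EOT, or that one of the three sites will close all of its patients. Nothing says so; the shares of one third and one half are illustrations. Nor should the no-deaths-on-treatment figures be read as typical, since they are the extreme of the range.

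**Conclusion.** The concern holds as a conflict within the protocol. The analysis section requires survival and progression follow-up to study termination. The phases, calendar and EOT section stop about 30 days after the last dose, two places describe that point as the end of the study, and the exit rules send similar patients either off treatment or off the study.

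The effect on OS is conditional. Where patients are closed at EOT and the later death hazard is higher, median OS is expected to be too long by about 0.2 to 1.2 months (one third closed) or about 0.3 to 2.2 months (half closed). These sizes rest on exponential times and on the assumed medians above. ORR and the Simon decision are unaffected, and PFS and duration of response change little. The protocol should be corrected because the remedy is cheap and lost survival contacts may not be recoverable, but the point does not threaten the primary conclusion.

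**What to change.** 1. Replace study with study treatment in the synopsis discontinuation lead-in, the Table 2 notes and the later sentence of 6.3.2. Keep withdrawal of consent and sponsor termination as study-level exits, and record whether consent is withdrawn from treatment only or also from follow-up.
2. Relabel the synopsis final visit, and the phrase in 6.3.1 that equates EOT with finishing the study, as end of treatment.
3. Add a follow-up phase to 3.1.1 and a post-EOT column to Section 5. Collect survival status by phone or chart, for example every 12 weeks, until death, withdrawal of consent to follow-up or study termination, as 11.6 says. For patients who stop without progression, collect routine paraprotein results until progression or new therapy.

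The interval is for the sponsor to set. A fixed cut-off shorter than study termination would require 11.6 to be changed as well.

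**Cost.** Wording in five places, one phase and one column. Contacts per patient are roughly mean survival after treatment divided by 12 weeks (2.76 months). Assumed medians of 4 to 12 months give means of 4/ln2 = 5.8 to 12/ln2 = 17.3 months, so about 2.1 to 6.3 brief contacts if everyone is followed to death, or about 61 to 182 for the 29 phase II patients. Earlier termination lowers this. The final OS report would come later.

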### **6.1 Study Assessments**

#### **6.1.1 Efficacy Assessments**

The clinical activity of selinexor will be evaluated for its effects on disease response criteria in terms of best response, duration of response, progression-free survival (PFS) and overall survival (OS). Disease status will be measured by the uniform response assessment of the International Myeloma Working Group.

The baseline disease assessment must be recorded and measured within 28 days prior to treatment start. During the treatment period, disease assessments will be performed every cycle, and as clinically indicated.

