### 6.2.3 End of Treatment

Patients who discontinue therapy for any reason must have an end of treatment (EOT) visit completed 30 days (± 7 days) after the last application of study drug.

At the EOT visit, the patients will undergo the following assessments:

Pregnancy test (if applicable)	A serum pregnancy test will be performed in pre-menopausal women and women who are post-menopausal for < 2 years to exclude that a pregnancy occurred under treatment
Physical examination and vital signs	
 
• Body weight
 
• Blood pressure, pulse, temperature
 
• Physical examination
 

Cardiac evaluation	12-lead ECG, echocardiogram or MUGA
Hematology	Hemoglobin, white blood cell (WBC) count, absolute neutrophil count and platelet count
Clinical chemistry	Sodium, potassium, chloride, bicarbonate, BUN, creatinine, glucose, calcium, phosphate, magnesium, ALT, AST, alkaline phosphatase, total bilirubin, total protein, albumin, LDH
Assessment of disease status	The disease status will be assessed by serum protein electrophoresis, 24h urine for protein electrophoresis and serum free light chain assay
Adverse events and concomitant medication	Assessed on an ongoing basis
Bone Marrow biopsy and Aspirate	A bone marrow aspiration and biopsy will be obtained at the end of treatment and before the initiation of another therapy in patients with progressive disease

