Progressive disease (PD) f	Requires only one of the following: Increase of $\geq 25\%$ from baseline in: 
 
 Serum M-component and/or (the absolute increase must be <math>\geq 0.5</math> g/dl)g
 
 Urine M-component and/or (the absolute increase must be <math>\geq 200</math> mg/24 hours)
 
 the difference between involved and uninvolved sFLC levels (In patients without measurable serum and urine M-protein levels), the absolute increase must be <math>> 10</math> mg/dl.
 
 the size of existing bone lesions or soft tissue plasmacytomas as well as definite development of new bone lesions or soft tissue plasmacytomas
 
 Development of hypercalcemia (corrected serum calcium <math>> 11.5</math> mg/dl) that can be attributed solely to the plasma cell disorder.
 

a. All response categories require two consecutive assessments made at anytime before the institution of any new therapy; all categories also require no known evidence of progressive or new bone lesions if radiographic studies were performed. Radiographic studies are not required to satisfy these response criteria.

b Confirmation with repeat biopsy not necessary.

c Presence/absence of clonal cells is based upon the  $\kappa/\lambda$  ratio by immunohistochemistry and/or immunofluorescence requires a minimum of 100 plasma cells for analysis. An abnormal ration reflecting presence of an abnormal clone is  $\kappa/\lambda$  of  $> 4:1$  or  $< 1:2$ .

d Applicable only to patients who have 'measurable' disease defined by at least one of the following three measurements: Serum M-protein  $\geq 0.5$  g/dl, Urine M-protein  $\geq 200$  mg/24hour, Serum FLC assay involved FLC level  $\geq 10$  mg/dl provided serum FLC ration is abnormal. e. Not recommended for use as an indicator of response; stability of disease is best described by providing the time to progression estimates).

f All relapse categories require two consecutive assessments made at anytime before classification as relapse or disease progression and/or the institution of any new therapy.

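### PFS for patients without an event runs to last follow-up, the same date as OS, although no disease assessment is scheduled after the end-of-treatment visit

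*Combined protocol and SAP*

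**What the plan says.** Section 11.6 (Analysis of the Phase II) states: "PFS is defined as the time from start of treatment to death of any cause, disease progression, or the date of last follow-up", taking the earliest. The next sentence defines OS with the same last-follow-up date. The section adds "The time-to-event data will be estimated using the Kaplan-Meier method" and, on follow-up, "Patients will be followed for survival and progression until termination of the study". It does not say which of the three dates are events and which are censoring dates, does not define last follow-up, and gives no rule for new anti-myeloma therapy or for stopping without progression. Duration of response is listed as a secondary endpoint in 11.1.2, but 11.6 gives it no start, end or censoring date.

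On assessments, section 6.1.1 says "During the treatment period, disease assessments will be performed every cycle, and as clinically indicated". Section 6.2.3 says "Patients who discontinue therapy for any reason must have an end of treatment (EOT) visit completed 30 days" after the last dose, with a 7-day window and with serum, urine and free-light-chain tests. The study calendar (section 5) has no column after that visit. Section 6.3.1 leaves later treatment to the investigator.

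Appendix A, footnote f, on progression reads: "All relapse categories require two consecutive assessments made at anytime before classification as relapse or disease progression and/or the institution of any new therapy". Footnote a, on response, reads: "All response categories require two consecutive assessments made at anytime before the institution of any new therapy".

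**The concern.** PFS and OS share one closing date, but they need different information. A telephone contact establishes that a patient is alive; it does not establish that the myeloma has not progressed. Patients can leave treatment without progression: section 6.3.2 lists adverse events, withdrawal of consent, intercurrent illness and investigator discretion, and section 8.1.3 adds prolonged toxicity delay. Inclusion criterion 3 requires disease refractory to the most recent therapy, so a further line of treatment after stopping is likely. Time with no myeloma test, or on another drug, can then be credited to this regimen.

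PFS is a named secondary endpoint of a single-arm trial with 29 patients in the phase II analysis, so a few such patients can move the curve. Two analysts who both follow 11.6 and Appendix A could report different PFS from the same data. Duration of response is exposed in the same way if it takes the same closing date.

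**Working it through.** **The plan's own figures.** The only design figures concern response rate. Continue if 3 or more of 13 respond; declare active if 8 or more of 29 do (16 in stage 2):

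P(active) = Σ over x = 3 to 13 of b(x; 13, p) × P(X₂ ≥ 8 − x; 16, p)

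- p = 0.40: 0.9069 (stated 90.7%); early stopping 0.0579 (stated 0.058)
- p = 0.15: 0.04999 (stated 0.05)

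All reproduce, and none uses PFS. The documents give no PFS median, event count or power, so what follows is illustration.

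**One patient, three answers.** Suppose a patient stops at month 2 without progression, has the end-of-treatment visit at about month 3, switches therapy then, progresses on the new drug at month 6 and is last contacted at month 14.

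| Reading | PFS record |
|---|---|
| Last disease assessment closes PFS | censored at about month 3 |
| Progression after the switch counts | event at month 6 |
| Progression after the switch not seen or not counted; last contact closes PFS | censored at month 14 |

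The text does not choose between these.

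**Model (all inputs assumed).** True median PFS is m months, so the progression hazard is λp = ln 2 / m. A share q stops without progression, with hazard λd = λp·q/(1 − q). After stopping, the next recorded event has hazard λ2. With a = λp + λd, the estimated curve is

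S(t) = e^(−at) + [λd/(a − λ2)] × [e^(−λ2·t) − e^(−at)]

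If later progression is not counted, λ2 is the death hazard. If it is counted, λ2 is the next-line progression hazard. Stopping is independent of progression in this model, so censoring at stopping returns m by construction.

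Example: m = 5, q = 20%, median survival after stopping 12 months. λp = 0.1386, λd = 0.0347, a = 0.1733, λ2 = 0.0578, and the bracketed ratio is 0.30.

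- S(5.30) = 0.399 + 0.30 × (0.736 − 0.399) = 0.500, so the median is 5.30 rather than 5.0.
- S(12) = 0.125 + 0.30 × (0.500 − 0.125) = 0.238, against a true e^(−0.1386 × 12) = 0.189.

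**Median if later progression is not counted (12-month survival after stopping):**

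| True median | q = 10% | 20% | 30% | 40% |
|---|---|---|---|---|
| 3 | 3.11 | 3.26 | 3.47 | 3.81 |
| 5 | 5.13 | 5.30 | 5.54 | 5.87 |
| 8 | 8.11 | 8.25 | 8.42 | 8.65 |

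Varying survival after stopping from 9 to 18 months, the smallest shift is 8.03 − 8 = 0.03 months (m = 8, q = 10%, 9 months) and the largest 9.30 − 8 = 1.30 (m = 8, q = 40%, 18 months).

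**At 12 months,** with q = 25% and 15-month survival after stopping: for m = 4 the median goes from 4.0 to 4.5 and 12-month PFS from 13% to 22%; for m = 6, from 6.0 to 6.5 and from 25% to 31%.

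**Median if later progression is counted (q = 40%):**

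| True median | Next-line median 3 | Next-line median 5 |
|---|---|---|
| 3 | 3.00 | 3.31 |
| 5 | 4.51 | 5.00 |
| 8 | 6.56 | 7.27 |

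The shift runs from 8 − 6.56 = 1.44 months lower to 0.31 higher.

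**At the trial's size.** Simulated trials of 29 patients (m = 5, 12-month survival after stopping, accrual over the 20 months given in section 3.2, data cut at an assumed 26 months) give typical Kaplan-Meier medians of 5.11, 5.30, 5.56 and 5.87 for q = 10, 20, 30 and 40%. Censoring at stopping gives 4.99 to 5.05.

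**The case against.** A reader might infer that Appendix A recognises only progression documented before any new therapy, so that everyone who switches gains progression-free time. The documents do not support that. Footnote f joins classification and new therapy with and/or, so two assessments made on the next regimen, before progression is classified, arguably qualify. The unqualified limit is in footnote a, which covers response.

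A reader might also take last follow-up to mean a survival contact. Section 11.6 leaves it undefined and says that progression is followed too, so month 6 is a natural reading of the example above. That defence is only partial, because no test after the end-of-treatment visit is scheduled to make such follow-up happen.

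Following patients through later therapy is a legitimate treatment-policy approach if later progression counts. Censoring at new therapy has its own weakness: it assumes that stopping is non-informative, which is doubtful if patients stop because they tolerate the regimen badly. This stands, and it makes the handling of new therapy a choice to be declared.

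Finally, PFS carries no hypothesis or decision rule, and the historical comparison in 11.6 concerns response rate. With 29 patients and a true median of 4 months, the simulated 95% sampling range of the median is about 2.2 to 6.5 months, so a half-month shift is well inside noise. That limits the consequence but does not justify an undefined censoring date.

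**Conclusion.** The point holds as a gap in the PFS definition. As written, a patient without an event can be carried progression-free to a date with no disease assessment, and the plan does not settle whether progression after a new therapy counts. If it is not observed or not counted, the median is inflated by about 0.03 to 1.3 months for true medians of 3 to 8 months, 10 to 40% stopping without progression and 9 to 18 months' median survival afterwards; the relative effect at 12 months is larger. These inputs, and the independence of stopping from progression, are assumptions. It would be wrong to conclude that the bias is always upward: with later progression counted, the shift can be nil or downward, or slightly upward where next-line PFS is longer. The response analysis, sample size and Simon rule do not change. For a secondary endpoint this should be corrected before analysis.

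**What to change.** In section 11.6:

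- State that death and confirmed progression are the PFS events, and that patients with neither are censored at their last adequate disease assessment. Keep last contact as the censoring date for OS only.
- Define duration of response and apply the same closing rule.
- State whether progression after new anti-myeloma therapy counts, and align footnote f of Appendix A with that choice.
- Pre-specify one handling of new therapy as the main analysis, for example censoring at the last adequate assessment before it. Make the alternative (counting later progression, or counting new therapy as an event) a sensitivity analysis.
- Record the start date of the next therapy. If later progression is to count, schedule disease assessments after the end-of-treatment visit.

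The core change costs a few sentences and one date field; assessments after the end-of-treatment visit would be an added burden. Some patients will be censored earlier, PFS may look slightly less favourable, and censoring at new therapy brings in the non-informative-stopping assumption, which is why the sensitivity analysis is needed.
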